7.5 Future Use of Study Data

The data collected in this study may be used to justify additional studies of variations on the Zenith® TX2® Low Profile Endovascular Graft including, but not limited to, design variations. It is anticipated that the safety and effectiveness data obtained may serve as prior information in the analysis of the safety and effectiveness of future variations of the Zenith® TX2® Low Profile Endovascular Graft.

8.0 Risk Analysis and Risk Assessment

Please reference the Clinical Investigator Brochure for a summary of the complete risk analysis.

8.1 Risks and Foreseeable Adverse Device Effects

Risks of adverse events are likely to be similar to those reported in recent studies of other endovascular thoracic aortic grafts. Adverse events associated either with the Zenith® TX2® Low Profile Endovascular Graft or the implantation procedure that may occur and require intervention include, but are not limited to:

- Amputation
- Anesthetic complications and subsequent related problems (e.g., aspiration)
- Aortic damage, including perforation, dissection, bleeding, rupture, and death
- Aortic valve damage
- Aortobronchial fistula
- Aortoesophageal fistula
- Arterial or venous thrombosis and/or pseudoaneurysm
- Arteriovenous fistula
- Bleeding, hematoma, or coagulopathy
- Bowel complications (e.g., ileus, transient ischemia, infarction, necrosis)
- Cardiac complications and subsequent related problems (e.g., arrhythmia, tamponade, myocardial infarction, congestive heart failure, hypotension, hypertension)
- Claudication (e.g., buttock, lower limb)
- Death
- Edema
- Embolization (micro and macro) with transient or permanent ischemia or infarction
- Endoleak
- Endoprosthesis: improper component placement, incomplete component deployment, component migration, suture break, occlusion, infection, stent fracture, graft material wear, dilatation, erosion, puncture, perigraft flow, barb separation, and corrosion
- Femoral neuropathy
- Fever and localized inflammation

- Genitourinary complications and subsequent related problems (e.g., ischemia, erosion, fistula, incontinence, hematuria, infection)
- Hepatic failure
- Impotence
- Infection of device or access site, including abscess formation, transient fever, and pain
- Lymphatic complications and subsequent related problems (e.g., lymph fistula, lymphocele)
- Neurologic local or systemic complications and subsequent related problems (e.g., stroke, transient ischemic attack, paraplegia, paraparesis/spinal cord shock, paralysis)
- Occlusion of coronary arteries
- Pulmonary embolism
- Pulmonary/respiratory complications and subsequent attendant problems (e.g., pneumonia, respiratory failure, prolonged intubation)
- Renal complications and subsequent related problems (e.g., artery occlusion, contrast toxicity, insufficiency, failure)
- Surgical conversion to open repair
- Vascular access site complications, including infection, pain, hematoma, pseudoaneurysm, arteriovenous fistula
- Vascular spasm or vascular trauma (e.g., iliofemoral vessel dissection, bleeding, rupture, death)
- Vessel damage
- Wound complications and subsequent related problems (e.g., dehiscence, infection)

8.2 Methods to Minimize Risks

This device will be used only by trained physicians who are experienced in the study procedure. Patients will be selected according to the inclusion/exclusion criteria outlined in this document.

The device design, non-clinical testing, clinical study design, and the Instructions for Use are intended to minimize the risks associated with the endovascular procedures.

9.0 Safety Monitoring and Event Reporting

9.1 Data Safety Monitoring Board

A Data Safety Monitoring Board (DSMB) consisting of independent physicians, who are not investigators in the investigation and who do not have a perceived conflict of interest with the conduct and administration of the investigation, will be convened on a regular basis to evaluate investigation progress and review adverse events.

9.2 Clinical Events Committee

An independent Clinical Events Committee (CEC) consisting of physicians, who are not investigators in the investigation and who do not have a perceived conflict of interest with the conduct and administration of the investigation, will be established to adjudicate clinical events reported during the investigation. This adjudication will be performed according to standard operating procedures to assess whether the events were due to a pre-existing or unrelated condition, or were procedure-related, technique-related, and/or device-related.

Regularly scheduled review/monitoring of all patient data will be conducted at the Data Coordinating Center, in part, for identification of adverse events and assurance that they are correctly reported to the DSMB and CEC.

9.3 Adverse Event Reporting

Adverse events are to be reported to the Data Coordinating Center using the appropriate case report form. In cases of adverse device effects or serious adverse events, completed forms should be submitted to the Data Coordinating Center as soon as possible upon knowledge of the event.

The Data Coordinating Center will review the information submitted for possible reporting to the Sponsor. The Sponsor shall, if required according to applicable regulations, report the event to the appropriate Regulatory Authority. The Principal Investigator or designee will notify his/her Ethics Committee (EC)/Institutional Review Board (IRB) of applicable events according to institutional guidelines. If indicated, all investigators/sites will be notified by the Sponsor.

10.0 Administrative

10.1 Data Collection

Patient data will be collected and entered by the investigative site into an electronic case report form (eCRF) system. This is a secure, web-based system, allowing those with permission to access data from any location at any time. Site personnel are required to have unique login names and passwords in order to enter patient data, and, in accordance with 21 CFR Part 11, the eCRF system creates a secure, computer-generated, time stamped audit trail to record the date and time of operator entries and actions that create, modify, or delete electronic records.

10.2 Data Management and Quality Assurance

Each principal investigator or appropriately trained designee shall enter clinical data into the electronic data capture system. Investigators will provide all applicable clinical data and documentation to the Sponsor. Patient data and documents pertaining to the investigation will be kept and archived by the Sponsor. Data will be reviewed for missing data, data consistency, and reasonableness of responses. Discrepancies will be resolved through a formal query process involving direct contact with investigators or research coordinators. Standard operating procedures will be followed for database management, data verification, and data archiving and retention.

As needed to assist the Sponsor in its research (e.g., during evaluation of an adverse event), data will be accessible to the Sponsor, the participating investigators, the manufacturer, and companies or individuals the Sponsor authorizes.

Pertinent imaging (pre-procedure, procedural, and follow-up) will be sent to MED Institute, Inc., which will coordinate shipment of imaging for independent analysis by the core laboratory.

10.3 Data Reporting

Progress reports and a final report at the conclusion of the clinical investigation will be submitted by the investigators and Sponsor to the regulatory bodies and IRBs/ECs as required by local regulations.

10.4 Emergency Situations and Vulnerable Subjects

Patients will not be treated with the Zenith® TX2® Low Profile Endovascular Graft in emergency situations where prior consent of the patient or the patient's legally-authorized representative in accordance with 21 CFR Part 50 is not possible.

10.5 Criteria and Procedures for Withdrawal

Subjects may withdraw from the study at any time without penalty or loss of benefits. The investigator may also decide to withdraw a subject from the study at any time on the basis of medical judgment. The investigator must make a reasonable effort to ascertain and record the reason for withdrawal or discontinuation for each patient while fully respecting the patient's rights. The reasons for withdrawal and discontinuation of any patient from the investigation shall be recorded. If such discontinuation is because of problems with safety or lack of effectiveness, that patient shall still be followed up in the investigation, if possible.

10.6 Deviations from Clinical Investigation Plan

Investigators are not allowed to deviate from this clinical investigation plan (CIP) without prior authorization by the Sponsor except under emergency situations when necessary to preserve the rights, safety, and well-being of human subjects. Deviations and non-compliances will be recorded together with an explanation. Deviations or non-compliances that impact the rights, welfare, or safety of patients shall be reported to the Sponsor, regulatory authorities, and IRB/EC as required.

10.7 Early Termination or Suspension of the Investigation

The Sponsor reserves the right to terminate/suspend the study at any point should they believe that important harmful events might result from its continuation.

10.8 Limitations of the Investigation

This study is inherently limited by the number of patients who will be excluded due to general, medical, and anatomical exclusion criteria. Additional challenges to the study include the anticipated comorbidities, which may confound data analysis

10.9 Publication Policy

Publication policy, rights, and obligations for this investigation have been negotiated, detailed, and defined in the Investigation Contractual Documents and Agreements with the Investigation Site and Investigators.

10.10 Approvals and Agreements

The Sponsor, coordinating investigator (if applicable), and the principal clinical investigators for each site shall agree to this document and any modifications. A justification for any modification will be documented. Approval and agreement will be indicated by signing and dating the signature page provided with this document.

10.11 General Information

10.11.1 Sponsor

The Sponsor for this investigation is Cook Incorporated. See Appendix A for contact information.

10.11.2 Manufacturer

The Manufacturer for this investigation is William Cook Europe, ApS. See Appendix A for contact information.

10.11.3 Data Coordinating Center/Monitor

The Data Coordinating Center for this study is MED Institute, Inc. See Appendix A for contact information.

10.11.4 Investigation Compliance

This investigation shall be performed according to the Declaration of Helsinki and 21 CFR 812.

The investigator is responsible for obtaining approval of this clinical investigation by the relevant EC/IRB. The Sponsor must be provided with a copy of this approval before delivery of any study device. Furthermore, the investigator will ensure that local regulations concerning data protection are followed. Additional requirements imposed by an IRB, EC, and/or regulatory authority shall be followed, if appropriate.

10.11.5 Investigators

A complete list of the coordinating clinical investigator, principal clinical investigators, and clinical investigators, along with their contact information, will be updated and maintained by the Data Coordinating Center.

10.11.6 Monitoring Arrangements

The monitor for this investigation is MED Institute, Inc. See Appendix A for contact information. Written procedures for monitoring the investigation are maintained by the monitor and can be found in Appendix B.

10.11.7 Exposition of the Clinical Investigation Plan

In case of translation of the Clinical Investigation Plan into the language of the participating countries, the English version is to be considered as the original, i.e., when expounding the contents of the Clinical Investigation Plan in these languages, the English version is definitive in cases of doubt.

APPENDIX B
Written Procedures for Monitoring Investigations

Written Procedures for Monitoring Clinical Investigations

A. Selection of the monitor.

Designated by the sponsor to oversee the investigation, the monitor may be an employee of Cook, an employee of a monitoring organization (CRO), or an independent contractor or consultant. The monitor shall be qualified by training and experience to monitor the investigation in accordance with all applicable regulations and standards for conducting clinical investigations.

B. General duties of the monitor.

The monitor must ensure that the investigation is conducted in accordance with:

1. The signed investigator agreement.
2. The clinical investigation plan (CIP)/protocol.
3. Any conditions imposed by the IRB/EC or regulatory authority.
4. The requirements of the applicable regulations and standards.

C. Reports by the monitor to the sponsor.

1. Any noncompliance with the items listed above. In the event that the investigator is not complying with the requirements outlined above, it is the sponsor's responsibility to secure compliance.
2. Any adverse events or effects that are potentially reportable to a regulatory authority.

D. Initiating the investigation.

Prior to initiating any clinical use of the device, the monitor or sponsor representative will participate in a pre-investigation or initiation visit with each investigative site.

At a minimum, the following items shall be addressed during the site initiation visit:

- Provide training to investigator on his/her responsibilities per the investigator agreement, applicable laws, regulations, and standards; and
- Provide training to investigator that the IRB/EC approval letter and informed consent/patient information is on file before initiation of the clinical investigation.

Additionally, training may be provided to the investigator on:

- The regulatory status of the device/product(s) and the requirements for the accountability of same;

- The nature of the clinical investigation plan (CIP);
- The requirements for an adequate and well-controlled clinical investigation;
- His or her obligation to obtain informed consent in accordance with applicable regulations;
- His or her obligation to ensure continuing review of the clinical investigation by the IRB/EC in accordance with conditions of approval and applicable regulations and to keep the sponsor informed of such IRB/EC approval and subsequent IRB/EC actions concerning the investigation;
- The importance of access to an adequate number of suitable subjects to conduct the investigation;
- The importance of adequate facilities for conducting the clinical investigation; and
- The importance of sufficient time from other obligations to carry out the responsibilities to which the investigator is committed by applicable regulations.

E. During the course of the investigation, at the direction of the Project Manager, the monitor should visit the site frequently enough to ensure that:

- The facilities and research staff used by the investigator continue to be acceptable for purposes of the clinical investigation;
- The applicable version of the CIP and agreements are being followed;
- Changes to the CIP, informed consent/patient information have been approved by the IRB/EC and/or reported to the sponsor and the IRB/EC;
- Accurate, complete, and current records are being maintained;
- Accurate, complete, and timely reports are being made to the sponsor and IRB/EC; and
- The investigator is carrying out the agreed-upon activities and has not delegated them to other previously unspecified staff.

As appropriate, the following tasks could be performed during periodic visits:

- Device/product accountability review;
- Adverse event review to ensure that events are appropriately reported within the time periods required by the sponsor, CIP, IRB/EC, and applicable regulatory requirements; and
- Source data verification per the monitoring plan to determine that:
 - Informed consent/patient information has been documented in accordance with applicable regulations and expectations of the local IRB/EC;

- The information recorded in the case report forms (CRFs; paper or electronic) is complete, accurate, and legible;
- There are no omissions in the CRFs of specific data elements, such as the administration to any patient of concomitant test articles or the development of an intercurrent illness;
- Missing visits or examinations are noted; and
- Subjects failing to complete the clinical investigation and the reason for each failure are noted.

F. Records of the monitor.

The monitor shall prepare and maintain records of each initiation visit and each periodic visit, general site contact, or discussion. These will include:

1. Date, name, and address of the investigator, and names of other staff members present at each meeting.
2. A summary of the findings of the visit.
3. A statement of any action taken by the monitor or investigator to correct any deficiencies noted.
4. The monitor shall immediately notify the sponsor of any conditions of non-compliance with the protocol, clinical investigation plan, conditions of IRB/EC or regulatory authority approval, or the applicable regulations.

APPENDIX C
Definitions

Definitions

Aortic-injury-related

Mortality:	Any death determined by the independent clinical events committee to be causally related to the initial implant procedure, secondary intervention, or rupture of the transected aorta.
Barb Separation:	Radiographic evidence of detachment of barbs from the stent strut.
Calcification:	Fixation zone and iliac artery calcification will be graded based upon the following: None: Lack of calcification; Mild: Less than 40% circumferential calcification; Moderate: 40-70% circumferential calcification; Severe: Greater than 70% circumferential calcification; or Prohibitive: Severe and cannot be resolved in the opinion of the investigator.
Clinical Utility Measures:	Number of ventilator days; days to resumption of oral fluids; days to resumption of normal diet; days to resumption of normal bowel function; duration of ICU stay; days to discharge.
Device Infolding:	Infolding upon deployment due to anatomic constraint (i.e., device oversizing). ⁵
Device Compression/ Collapse:	Failure of the device to maintain its intended expanded diameter after implantation as a result of the dynamic application of external forces (i.e., blood flow). ⁵
Type I Endoleak:	A peri-prosthetic leak occurring at the proximal and/or distal fixation zones.

Type II Endoleak:	A leak caused by retrograde flow from patent vessels. Type IIa includes significant subclavian, celiac, or anomalous vertebral arteries. Type IIb includes bronchial and intercostal artery involvement or minor leaks.
Type III Endoleak:	A leak caused by a defect in the graft fabric, or inadequate seal between modular components.
Type IV Endoleak:	A leak caused by graft fabric porosity, often resulting in a generalized blush of contrast into the injury.
Unknown Endoleak:	Continuing blood flow into the injury with undefined origin.
Injury Severity Score:	The Injury Severity Score (ISS) is an anatomical scoring system that provides an overall score for patients with multiple injuries. Each injury is assigned an Abbreviated Injury Scale (AIS) score and is allocated to one of six body regions (head, face, chest, abdomen, extremities (including pelvis), external). Only the highest AIS score in each body region is used. The 3 most severely injured body regions have their scores squared and added together to produce the ISS score.
Major Adverse Events:	All-cause death; stroke; paraplegia; Q-wave MI; cardiac event involving arrest or resuscitation; renal failure requiring permanent dialysis, hemofiltration, or kidney transplant in a patient with a normal pre-procedure serum creatinine level; conversion to open repair; pulmonary embolism involving hemodynamic instability or surgery; graft infection; or wound complication requiring return to the operating room.

- MI (Non-Q-Wave): Clinical evidence of a myocardial infarction with elevated peak CK values greater than or equal to three times the upper limit of normal with elevated CK-MB (above the institution's upper limit of normal) in the absence of new pathological Q-waves or clinical evidence of a myocardial infarction with troponin greater than three times the upper limit of normal, as determined by the investigator.
- MI (Q-Wave): Requires one of the following criteria:
- Post-procedure chest pain or other acute symptoms consistent with myocardial ischemia and the presence of new pathological Q-waves in two or more contiguous ECG leads in the absence of timely cardiac enzyme data.
 - New, post-procedure pathological Q-waves in two or more contiguous ECG leads and elevation of cardiac enzymes.
- Occlusive Disease: Fixation zone and iliac artery occlusive disease will be graded based upon the following:
None: Lack of occlusive disease;
Mild: Some disease, focal with less than 30% narrowing;
Moderate: 30-50% narrowing not requiring interventional techniques to meet inclusion criteria;
Severe: Greater than 50% or any patient requiring angioplasty prior to endograft delivery; or
Prohibitive: Severe and cannot be resolved in the opinion of the investigator.
- Migration (radiographic): Core laboratory determination of antegrade or retrograde movement of the proximal component of the endoprosthesis > 10 mm relative to anatomical landmarks identified on the first post-operative CT scan.

Migration (clinical):	Antegrade or retrograde movement of the proximal component of the endoprosthesis resulting in the need for a secondary intervention.
Renal Failure:	Acute or progressive renal insufficiency leading to the need for dialysis or hemofiltration.
Stent/Attachment System	
Fracture/Break:	Fracture or breakage of any portion of the stent or attachment system including metallic fracture or breakage of any suture material used to construct the stent or secure the stent or attachment system to the graft material.
Stroke:	Permanent clinically significant central nervous system deficit.
Success, Device (30-day):	Technical success, with none of the following at 30 days: 
• Device collapse;• Type I or type III endoleak requiring reintervention; or• Conversion to open surgical repair.
Success, Technical:	Successful access of the injury site and deployment of the Zenith® TX2® Low Profile Endovascular Graft in the intended location. The endovascular graft must be patent at the time of deployment completion as evidenced by angiographic imaging.

- Tortuosity: Fixation zone and iliac artery tortuosity will be graded based upon the following:
None: Lack of tortuosity;
Mild: Fairly straight arteries;
Moderate: Angulation manageable with stiff wires, < 70 degrees;
Severe: Angulation difficult, may require surgical exposure for straightening, not straightened entirely with wires; or
Prohibitive: Severe and cannot be resolved in the opinion of the investigator.
- Traumatic Aortic Injury: Injury will be graded based upon the following^{8,17}:
Grade 1: Intimal tear;
Grade 2: Intramural hematoma/large intimal flap (LIF);
Grade 3: Pseudoaneurysm; or
Grade 4: Rupture.

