5.2 Endpoints

The primary safety endpoint will be all-cause and aortic-injury-related mortality at 30 days.

The primary effectiveness endpoint will be device success, defined as technical success (i.e., successful access of the injury site and deployment of the Zenith® TX2® Low Profile Endovascular Graft in the intended location, and endovascular graft patency upon completion of deployment) with none of the following at 30 days:

- Device collapse;
- Type I or type III endoleak requiring reintervention; or
- Conversion to open surgical repair.

The secondary endpoints include an assessment of the following:

- At the intra-operative and post-procedure time points:
 - Procedural time and clinical utility measures (see Appendix C, Definitions);
- Through the 5-year time point:
 - Major adverse events (see Appendix C, Definitions),
 - Injury healing (as determined by maximum transverse diameter at the site of injury),
 - Secondary interventions,
 - Endoleak,
 - Device migration,
 - Device patency,
 - Device integrity, and
 - Device collapse.

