6.7 Post-operative Treatment of Endoleaks

Type I and type III endoleaks warrant immediate treatment. Type II endoleaks should be treated at the physician’s discretion, depending on endoleak source and time from implantation. Type III endoleaks should be treated with additional ballooning or prostheses.

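### 30-day device success checks patency only at completion of deployment, so a graft that later occludes, or migrates and is re-treated, can still count as a primary-endpoint success

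*Combined protocol and SAP*

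**What the plan says.** Section 5.2 and Appendix C give the same rule. Device success is "Technical success, with none of the following at 30 days": collapse, a qualifying endoleak, or conversion to open repair. The endoleak item reads "Type I or type III endoleak requiring reintervention; or", so the leak must be of type I or III and must also lead to reintervention.

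Technical success has a placement part, "Successful access of the injury site and deployment of the Zenith® TX2® Low Profile Endovascular Graft in the intended location", and a patency part. The patency part is fixed to the end of deployment: "endovascular graft patency upon completion of deployment" in Section 5.2, and in Appendix C "The endovascular graft must be patent at the time of deployment completion as evidenced by angiographic imaging". Neither place asks for patency again at 30 days.

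Three other definitions matter:
- Appendix C defines collapse as the device losing its intended expanded diameter under external forces. That does not describe thrombotic occlusion.
- Appendix C defines clinical migration as "Antegrade or retrograde movement of the proximal component of the endoprosthesis resulting in the need for a secondary intervention". It is not on the failure list.
- Reintervention is not defined anywhere.

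Patency, migration, endoleak and secondary interventions are separate secondary endpoints through 5 years (Section 5.2). All endpoints are analysed descriptively (Sections 3.3 and 7.2).

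**The concern.** The endpoint carries a 30-day label, but its patency check ends in the procedure room. The protocol foresees the events that are left out. Section 8.1 lists occlusion and component migration of the endoprosthesis among possible adverse events, and Section 6.8 expects some secondary interventions for migration. The information will be available: Section 5.3 collects patency and migration at follow-up, and Table 2 schedules CTA at 30 days.

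The list also treats similar events differently. Reintervention for a type I or III endoleak is a failure, while reintervention for an occluded or migrated graft is not, and no reason is given. At stake is the one primary effectiveness proportion. It could read higher than the share of patients whose graft was open and in place without re-treatment at 30 days. Section 7.5 expects the effectiveness data to serve as prior information for later device variations, so an inflated rate could be carried forward.

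**Working it through.** **Step 1: apply the definition to each course of events.** This uses Section 5.2 and Appendix C only.

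| Course up to day 30 | Score under the text | Deciding item |
|---|---|---|
| Occlusion caused by collapse | Failure | Collapse |
| Occlusion ending in open conversion | Failure | Conversion |
| Occlusion without collapse or conversion, reopened or still occluded | Success | No item applies |
| Migration with a type I/III endoleak requiring reintervention | Failure | Endoleak item |
| Migration ending in open conversion | Failure | Conversion |
| Migration re-treated without a qualifying endoleak or conversion | Success | No item applies |
| Extra prosthesis at the index procedure because the graft was not in the intended location | Failure | Technical success |
| Extra prosthesis at the index procedure for a type I/III endoleak | Not determined | Reintervention undefined |

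The third and sixth rows are the gap. The last row is an ambiguity.

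**Step 2: does any stated figure depend on the definition?** The only sizing figure is in Section 7.1, with p = 0.076, margin 0.08 and z = 1.96:

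n = z² p(1 − p) / margin² = 1.96² × 0.076 × 0.924 / 0.08² = 42.15, rounded up to 43.

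This reproduces the plan's 43 (50 enrolled). The p is 30-day mortality. The Appendix E rows sum to 112/1477 = 7.58%, which matches the stated 7.6%. Device success does not enter, so changing its definition leaves the sample size alone.

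**Step 3: size of the effect.** One patient moved from success to failure changes the rate by 1/50 = 2.0 points (1/43 = 2.3 points at 43 analysable patients). The documents give no rate for these events, so both the starting value of 49/50 and the number moved are assumptions. Exact (Clopper-Pearson) 95% limits for s successes in n are the 0.025 quantile of Beta(s, n − s + 1) and the 0.975 quantile of Beta(s + 1, n − s).

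| Patients moved | Device success | Exact 95% CI |
|---|---|---|
| 0 | 49/50 = 98% | 89.4% to 99.9% |
| 1 | 48/50 = 96% | 86.3% to 99.5% |
| 2 | 47/50 = 94% | 83.5% to 98.7% |
| 3 | 46/50 = 92% | 80.8% to 97.8% |

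**The case against.** The best defence is that this is a deliberate composite. It covers collapse (the device problem named in Section 2.3), seal failure and conversion. Occlusion and migration are prespecified secondary endpoints, the analysis is descriptive, and no success threshold could be passed wrongly. Much of that stands: the events would be visible in the report, and no test or decision rule is affected. It does not remove the gap, because the secondary tables leave the primary proportion unchanged. In a descriptive study with a single primary effectiveness endpoint, that proportion is the main effectiveness result.

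A reader might infer more than the documents support, in three ways:
- **That every occluded or migrated graft counts as a success.** The table shows several routes that already fail.
- **That an extra prosthesis at the index procedure is always scored as a success, crediting the study graft with another device's result.** The text does not settle this. Poor placement fails technical success, and an endoleak case turns on the undefined term. Section 6.7 does not help: "Type III endoleaks should be treated with additional ballooning or prostheses" stands under post-operative treatment, and a type III leak re-treated within 30 days is already a failure. The added prosthesis could also be a second study graft.
- **That any secondary intervention should be a failure.** Section 6.7 leaves type II endoleak treatment to the physician's discretion, so so broad a rule would turn discretionary treatment into device failure.

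It is also fair to say that the size shown is hypothetical. The arithmetic gives the weight of one patient, not evidence that such patients are expected.

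**Conclusion.** The point holds in a limited form. Section 5.2 and Appendix C agree with each other, and under both a graft can lose patency by day 30, or migrate and be re-treated, and still be a primary-endpoint success, provided there is no collapse (for occlusion), no qualifying endoleak (for migration) and no conversion. The possible overstatement is 2 percentage points per patient at N=50, and the number of such patients is unknown. The sample size of 43, with 50 enrolled, is unaffected. Scoring of an additional prosthesis at the index procedure is a secondary matter: the plan needs a definition there, but the text does not show a wrong result. The conclusion rests on reading the failure list as complete, which is how both places present it.

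**What to change.** In Section 5.2 and Appendix C, add to the 30-day failure list:

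- (a) loss of study-graft patency on the 30-day imaging or on earlier imaging;
- (b) secondary intervention within 30 days for occlusion or migration of the study graft, with discretionary type II endoleak treatment stated not to count.

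If the current definition is kept for comparability, report this stricter device success beside it as a prespecified supportive result.

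Separately, define reintervention, and state whether an additional prosthesis placed at the index procedure for a type I or III endoleak falls under it, so that all such patients are scored alike.

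**Cost.** Items (a) and (b) use data that Section 5.3 already collects, and no patients are added. The success rate may be slightly lower. Item (a) needs a scoring rule for patients without contrast CT, since the Table 2 footnote allows MR, non-contrast CT or TEE. Section 7.4 already allows investigator readings, clinical sequelae or later imaging to stand in for missing core laboratory assessments, and the rule could build on that. The index-procedure definition may need a case report form field for the reason an extra device was used. Section 4.3 covers products under investigation and does not clearly capture other devices.
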